9.4.3. Baseline Characteristics and Medical History

Baseline characteristics include ECOG performance status, duration from initial diagnosis, response to previous therapy, types of prior therapy, and height/weight/BSA. Baseline data will be tabulated for the same categories as used for demographics, using summary statistics; no formal hypothesis testing of dose cohort differences will be performed. Medical history and physical examination results at baseline will be tabulated by treatment cohort.

9.5. Efficacy Analysis

Disease response will be evaluated according to RECIST 1.1 (advanced solid malignancies) [Appendix 4](#)) or Lugano Classification (NHL) ([Appendix 3](#)) and will include the following endpoints: Time-to-event efficacy endpoints will be performed using the same Kaplan-Meier method for estimation of summary statistics, and will include the 25th, 50th (median) and 75th percentiles, associated two-sided 95% Cis (if estimable), and number of events and censored observations.

- Overall response rate (ORR): The analysis of ORR will be performed by calculating the point estimate of the percentage of patients who have either CR or PR, presented as the number and percentage of patients, including a two-sided 95% CI.
- Duration of response (DOR): the duration of time from first meeting CR or PR measurement criteria (whichever occurs first) until the first date that Progressive Disease (PD) recurrence is objectively documented. Patients without documented PD will be censored on the date of last disease assessment.
- Disease control rate (DCR): The analysis of DCR will be similar to that described for ORR, for patients who achieve CR, PR, or SD for ≥ 16 weeks.
- Duration of disease control: the duration of time from date of first study treatment until the first date the PD is objectively documented. Patients without documented disease progression will be censored on the date of last disease assessment.
- Progression-free survival (PFS): the duration of time from date of first dose of study treatment until the first date that PD is objectively documented or death due to any cause. Patients without documented PD will be censored on the date of last disease assessment.
- Overall survival (OS): the duration of time from date of first dose of study treatment until death from any cause. Patients who withdraw from the study or are alive at the time of data analysis will be censored on the date of last contact.

- TTP: The duration of time from date of first dose of study treatment to date of PD. Patients who withdraw from the study or are alive at the time of data analysis per Section 2.2.2 without documented DD will be censored on the date of last contact.

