2.2.2. Efficacy Endpoints

Disease response will be evaluated according to RECIST 1.1 (advanced solid malignancies and melanoma ([Appendix 4](#))) or Lugano Classification (NHL) ([Appendix 3](#)) and will include the following:

- **Overall response rate (ORR):** = proportion of patients who have a response of partial response (PR) or complete response (CR).
- **Duration of response (DOR):** the duration of time from first meeting CR or PR measurement criteria (whichever occurs first) until the first date that PD recurrence is objectively.
- **Disease control rate (DCR):** DCR = proportion of patients who have a response of CR, PR, and Stable Disease (SD) ≥ 16 weeks.
- **Duration of disease control:** the duration of time from date of first study treatment until the first date that PD is objectively documented.
- **Progression-free survival (PFS):** the duration of time from date of first study treatment until the first date that PD is objectively documented or death due to any cause.
- **Overall survival (OS):** the duration of time from date of first study treatment until death from any cause .

- **Time to Progression (TTP):** The duration of time from date of first study treatment until the first date that PD is objectively documented or death due to PD.

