PD without a gap of 2 or more consecutively missed scheduled disease status assessment before progression	Date of PD	Event

 
No PD or death on or before
 
a. database cut,
 
b. withdrawal of informed consent,
 
c. lost to follow-up,
 
d. start of new antineoplastic treatment,
 
e. No PD or death before a gap of 2 or more consecutively missed scheduled disease status assessment
 
	Date of last adequate disease assessment on or prior to the earliest occurrence of the events (a. – e.) listed in the left column	Censored
whichever occurs first		

Table 4-3 TTP and Duration of disease control outcome and censoring definition

Situation	Date of event or censoring	Outcome
No baseline disease assessment	Date of first study treatment	Censored
No adequate post-baseline disease sassessment unless death due to dise progression occurs prior to first post-baseline assessment	ase	Censored
Death due to disease progression be PD without a gap of 2 or more consecutively missed scheduled dis status assessment before death		Event
PD without a gap of 2 or more consecutively missed scheduled dis status assessment before progression		Event
No PD or death due to disease progression on or before  a. Death due to reasons other t disease progression	han  Date of last adequate disease assessment on or prior to the earliest occurrence of the events (a. – f.) listed in the left column	Censored
b. database cut,		
c. withdrawal of informed con	sent,	
d. lost to follow-up,		
e. start of new antineoplastic treatment,		
f. No PD or death due to disea progression before a gap of more consecutively missed scheduled disease status assessment		
whichever occurs first		

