# 4.2. STATISTICAL METHODS FOR EFFICACY ENDPOINTS

Binary endpoints of ORR and DCR will be calculated by point estimate with a 95% confidence interval (CI) using the exact method.

For time to event endpoints of DOR, PFS, OS, duration of clinical benefit and duration of disease control, the number and percentage of patients who had an event will be reported.

Median event time with 95% CI will be summarized using Kaplan-Meier (KM) method. The KM curve for PFS will be provided by treatment arm.

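### Protocol 9.5 and the SAP give different event and censoring rules for time to progression, and neither document says which one holds

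*Protocol*

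**What the plan says.** Protocol 9.5 gives TTP in two sentences. The first sets the event: "TTP: The duration of time from date of first dose of study treatment to date of PD". The second says that patients who withdraw or are alive at analysis, with a reference to Section 2.2.2, and "without documented DD will be censored on the date of last contact". The abbreviation DD is not defined; PD is presumably meant.

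Protocol 2.2.2 and the synopsis run TTP "until the first date that PD is objectively documented or death due to PD". Neither gives a censoring date for it. SAP 1.3.1 and SAP Table 4-1 use the same event.

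SAP Table 4-3 holds a full rule. Censoring applies where there is "No PD or death due to disease progression on or before" any of a list of stopping points, which include "start of new antineoplastic treatment". The censoring date is the "Date of last adequate disease assessment on or prior to the earliest occurrence of the events". The TTP row of Table 4-1 does not refer to Table 4-3.

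SAP 4.2 lists the endpoints to be summarised: "For time to event endpoints of DOR, PFS, OS, duration of clinical benefit and duration of disease control". TTP is not among them, and duration of clinical benefit is defined nowhere.

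Protocol Section 9 requires changes from its analyses to be described in the SAP. SAP 1.7 states that there are none in the statistical section.

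**The concern.** TTP measures when disease progresses, and objective progression can be seen only at an assessment. Censoring at last contact keeps a patient in the risk set as progression-free for time in which nobody looked. The TTP censoring sentence in 9.5 has the form of the OS sentence just above it, where last contact is suitable. For DOR, duration of disease control and PFS, 9.5 censors at the last disease assessment.

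The event differs too. The censoring sentence in 9.5 covers only patients who withdraw or are alive. A patient who dies of the tumour before PD is documented is neither an event under the written definition nor covered by the censoring rule.

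A programmer therefore has two rules. TTP is a secondary endpoint in Parts A, B and C, and the synopsis lists it among the primary endpoints of the Dose Expansion, if that is conducted.

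**Working it through.** No sample size, power or decision rule rests on TTP, so there is no planned figure to reproduce. The check is a comparison of texts, a bound from the visit schedule, and an illustration.

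**1. The rules side by side**

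| Source | TTP event | TTP censoring date |
|---|---|---|
| Protocol synopsis and 2.2.2 | documented PD or death due to PD | none stated |
| Protocol 9.5 | PD | last contact (patients who withdraw or are alive) |
| SAP 1.3.1 and Table 4-1 | documented PD or death due to PD | none stated |
| SAP Table 4-3 | PD or death due to progression | last adequate disease assessment |

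Protocol 2.2.2 conflicts with 9.5 on the event only. The censoring conflict is between 9.5 and SAP Table 4-3.

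**2. Unscanned time that 9.5 can count**

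Inputs are from the footnotes to the protocol's schedules of assessments. The safety call is 30 days (+7) after the last dose. Follow-up is then every 3 months for 1 year (±7 days). Scans in this period are conditional on feasibility and clinical indication, with a telephone call as the fallback. The OS rule in SAP Table 4-1 gives a telephone contact as an example of a valid status date.

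- Last dose to last call: 30 + 365 = 395 days; with both windows, 30 + 7 + 365 + 7 = 409 days.
- From an end-of-treatment scan on day 14: 395 − 14 = 381 days.

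Rule 9.5 can count all of this as progression-free. Table 4-3 counts none of it if no scan is done.

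**3. Illustration of size (assumed inputs)**

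Assumptions: exponential progression with true median *m* weeks; scans every 8 weeks; exponential stopping for other reasons at a rate such that a share *f* would stop before true progression. Those who stop before PD is documented have no further scan and are telephoned to day 395. Deaths and new therapy are left out.

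Let a = 2^(−8/m) be the chance of no progression over one scan interval, and b = a^(f/(1−f)) the chance of not stopping. PD is documented at scan k with probability a^(k−1)(1−a)b^k. As 395/7 = 56.4 weeks, nobody is censored before week 56 under last contact. Up to week 48 the Kaplan-Meier estimate is therefore

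S(8K) = 1 − (1−a)b[1 − (ab)^K]/(1 − ab),

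and the telephone-only share is 1 − (1−a)b/(1−ab). With censoring at the last scan, patients who have stopped are not at risk at the next scan, so S(8K) = a^K, the true value.

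Example: m = 12, f = 0.1. Then a = 0.630, b = 0.950, ab = 0.598 and (1−a)b/(1−ab) = 0.3515/0.4016 = 0.875, a telephone-only share of about 12%. S(24) = 1 − 0.875 × (1 − 0.214) = 0.31, against 0.630³ = 0.25.

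With f = 0.1, 0.2, 0.3 and 0.4, each cell shows last assessment → last contact:

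| True median (weeks) | Telephone only | S(24) | S(48) | Kaplan-Meier median (weeks) |
|---|---|---|---|---|
| 12 | 12% | 0.25 → 0.31 | 0.06 → 0.16 | 16 → 16 |
| 12 | 25% | 0.25 → 0.38 | 0.06 → 0.27 | 16 → 16 |
| 12 | 37% | 0.25 → 0.46 | 0.06 → 0.38 | 16 → 24 |
| 12 | 49% | 0.25 → 0.54 | 0.06 → 0.50 | 16 → 48 |
| 20 | 11% | 0.44 → 0.47 | 0.19 → 0.25 | 24 → 24 |
| 20 | 23% | 0.44 → 0.50 | 0.19 → 0.33 | 24 → 32 |
| 20 | 34% | 0.44 → 0.54 | 0.19 → 0.40 | 24 → 32 |
| 20 | 46% | 0.44 → 0.59 | 0.19 → 0.49 | 24 → 48 |

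In the 20-week, 23% row, S(24) is 0.501, so the median only just misses week 24. The upper quartile under last assessment is 24 weeks (m = 12) or 40 weeks (m = 20). Under last contact it is 32 weeks in the first row and later than 48 weeks in all others. Simulation of 40,000 patients per row gave the same 24-week values to within 0.01.

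**The case against.** The strongest answer is that the SAP is later (September 2021, against March 2020 for the protocol) and already holds the sound rule, which would probably be programmed. This stands as to the likely result. It does not settle the documents, because SAP 1.7 says that nothing was changed and so gives Table 4-3 no declared precedence over 9.5.

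The 9.5 bullet also cites Section 2.2.2, so it may be meant to import that event, and DD looks like a slip. That is a fair reading of intent, but the written event is still PD only.

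The illustration is close to a worst case. The protocol requires an end-of-treatment scan for patients who stop for reasons other than progression, and provides for 3-monthly scans where feasible and clinically indicated. The calls ask about disease status, and protocol 6.9.3 treats the start of other anti-tumour therapy as an indication of progression. In a variant where half of the telephoned patients start new therapy counted as PD, the 24-week figure was 26–27%, against 23–24% under the SAP rule. The plan also reports medians and quartiles, not 24-week proportions. This all stands, and is why the percentages show direction and range only.

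A reader might infer that SAP 4.2 leaves TTP without a method. It does not: SAP Section 4 applies Kaplan-Meier to time-to-event efficacy endpoints generally, and Table 4-3 names TTP. The omission in 4.2 is a minor inconsistency.

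**Conclusion.** The conflict is real and should be resolved before analysis. Protocol 9.5 differs from 2.2.2, the synopsis and the SAP on the event, and from SAP Table 4-3 on the censoring date. The 9.5 rule, if applied, biases TTP upward, by an amount that grows with the share of patients followed by telephone only. The effect is mainly on the upper quartile and late progression-free proportions. The median is unchanged at about 11–12% telephone only, and moves by one 8-week scan or more from about 23% (true median 20 weeks) or 37% (true median 12 weeks). The documents do not give this share or the progression rate.

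Three stronger readings are tempting and are not supported. One is that reported TTP will be inflated; that requires the analyst to set Table 4-3 aside. Another is that 9.5 makes tumour deaths non-events; it states no outcome for a patient who dies of PD without documented PD. The third is that a TTP longer than PFS would itself show the error; TTP leaves out deaths from other causes by design.

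TTP is descriptive. Futility rests on response or stable disease, and MTD/RP2D selection on DLTs, safety and tolerability, so no trial decision depends on this point.

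**What to change.** - Make the SAP Table 4-3 rule the single TTP rule: the event is documented PD or death due to PD, with censoring at the last adequate disease assessment.
- State in SAP 1.7 that this replaces the TTP bullet of protocol 9.5. This line settles precedence without waiting for an amendment.
- Correct the TTP bullet in 9.5, including DD, at the next protocol amendment. An amendment for this alone would need IRB review.
- Point the TTP row of SAP Table 4-1 to Table 4-3.
- In SAP 4.2, list TTP and either remove or define duration of clinical benefit.

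The cost is a few words and no new data. Compared with the 9.5 rule, reported TTP may be slightly less favourable.

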9.5.1. Futility Testing

For Part A or Part B, at least one clinical response (minimum of stable disease ~16 weeks) must be seen in any of the first ten patients treated at the RP2D in order to fully enroll either expansion cohort. These 10 patients include the patients enrolled under the 3+3 design for DLT assessment; if necessary, additional patients will be enrolled to a maximum of 10 patients. If no clinical responses are observed, the study will be stopped for futility. If a clinical response is observed at any time, then enrollment of the full expansion cohort may proceed. Initiation of the KPT-9274 + niacin escalation will not be dependent upon demonstration of clinical benefit of the single agent, but futility at the KPT-9274 + niacin RP2D will be assessed prior to full expansion using the same criterion as described above for the single agent KPT-9274.

[figure not shown]

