# 1.6. INTERIM ANALYSIS

No interim analysis is planned for this study.

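### The futility rule tests each regimen at its own RP2D, but its only failure outcome is to stop the whole study

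*Protocol*

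**What the plan says.** The rule stands in the protocol synopsis (Dose Expansion Phase), protocol Sections 6.2.7 and 9.5.1, and SAP 1.1 (Dose Expansion Phase). Section 9.5.1 states these elements in order:

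- **Condition:** the rule is written for Part A or Part B. It asks for one or more responders, with stable disease of about 16 weeks as the minimum, among the first ten at the RP2D. Its stated purpose is "in order to fully enroll either expansion cohort".
- **Failure:** "If no clinical responses are observed, the study will be stopped for futility".
- **Pass:** "If a clinical response is observed at any time, then enrollment of the full expansion cohort may proceed".
- **Niacin regimen, start of escalation:** "Initiation of the KPT-9274 + niacin escalation will not be dependent upon demonstration of clinical benefit of the single agent".
- **Niacin regimen, expansion:** "futility at the KPT-9274 + niacin RP2D will be assessed prior to full expansion using the same criterion as described above for the single agent KPT-9274".

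Protocol Section 6.2.3 calls these checks futility analyses. SAP 1.6 states: "No interim analysis is planned for this study". SAP 1.7 says that nothing in the protocol's statistical section was modified.

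Part C (KPT-9274 + nivolumab in melanoma) has no futility rule. The synopsis makes its start depend on sufficient data from Part A.

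**The concern.** Two RP2Ds are to be declared, one for the single agent and one with niacin ER. The condition concerns patients at an RP2D, the pass releases a cohort, and the niacin RP2D is judged by itself. Only the failure outcome has no such limit. If one RP2D has no response in ten and the other has a responder, the paragraph gives two instructions that cannot both be followed: stop the study, and let the expansion cohort proceed.

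This is the trial's only efficacy stopping rule. Its scope decides whether a poor result in one group of ten closes only that regimen's expansion, or also closes the other regimen's expansion and a separate combination in melanoma. The SAP does not settle the matter. It repeats the sentence in SAP 1.1 and then says in SAP 1.6 that no interim analysis is planned.

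**Working it through.** **Scope of each element in Section 9.5.1**

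| Element | Scope as written |
|---|---|
| Opening words | Part A or Part B |
| Patients counted | First ten at the RP2D |
| One response seen | The full expansion cohort may proceed |
| Niacin RP2D | Its own assessment, same criterion |
| No response seen | The study |

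The last row is the only one that reaches beyond a regimen or cohort. Section 6.2.8 shows that a narrower form was available: its safety rule for the expansion phase ends in stopping enrolment into the expansion cohort.

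**Inputs for the size**

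- n = 10 per regimen and a pass at one or more responses (Section 9.5.1).
- True rate p of the futility event, which is stable disease of about 16 weeks or better. The documents give none, so 5% to 40% is assumed.
- Both RP2Ds are tested, and the two groups of ten are independent. Both are assumptions.

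The plan states no operating characteristic for this rule, so there is no figure to reproduce.

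**One regimen:** P(0/10) = (1 − p)^10.

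- 5%: 0.95^10 = 0.599
- 10%: 0.90^10 = 0.349
- 20%: 0.80^10 = 0.107
- 30%: 0.70^10 = 0.028
- 40%: 0.60^10 = 0.006

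**Two regimens, literal wording.** The study stops if either group has 0/10. With s1 and s2 the two single-regimen probabilities, P(stop) = 1 − (1 − s1)(1 − s2).

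For 5% paired with 30%: 1 − (1 − 0.5987)(1 − 0.0282) = 0.610.

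| True rate, other regimen | True rate, regimen of interest | Stopped by its own 0/10 | Stopped under the literal wording |
|---|---|---|---|
| 5% | 20% | 10.7% | 64.2% |
| 5% | 30% | 2.8% | 61.0% |
| 10% | 30% | 2.8% | 36.7% |
| 20% | 20% | 10.7% | 20.3% |

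Independence matters little in the 5% and 30% case. Whatever the dependence, the probability that at least one group fails lies between the larger single probability, 59.9%, and the sum, 59.9% + 2.8% = 62.7%.

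**Trigger.** Section 6.2.7 counts stable disease of about 8 weeks as a clinical response. The synopsis, Section 9.5.1 and SAP 1.1 say about 16 weeks. The two versions do not count the same patients as responders, so the rate to put into the formula depends on which version applies.

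**The case against.** The best defence is that the paragraph, read as a whole, is per regimen and a sensible team would apply it that way. Appendix 6 supports that intent: the rule answered a request that patients not enter the expansion cohorts without evidence of benefit. Section 5.1 also leaves termination to the sponsor's discretion, so an unintended automatic shutdown is unlikely. This is fair, and it limits the practical risk. It does not remove the conflict, because the failure sentence is explicit and appears in four places.

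Several stronger readings are tempting, and the documents do not support them.

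- *One arm's failure ends Part B as a question.* The start of the niacin escalation is expressly independent of single-agent benefit, and Section 6.2.7 places expansion after both escalations are complete. What is exposed is the other regimen's expansion.
- *The rule was meant to govern Part C.* It opens with Part A or Part B, the heading of Section 6.2.7 names Parts A and B, and Part C has its own start condition and safety review committee. Only the word *study* reaches Part C.
- *A response at one RP2D opens expansion at the other.* The phrase "in order to fully enroll either expansion cohort" invites this, but the paragraph's last sentence requires the niacin RP2D to be assessed before its own full expansion, which largely answers it. The phrase needs tidying only.
- *The SAP omits the rule.* SAP 1.1 states it in full. The look is a count with no test and no alpha, so the conflict with SAP 1.6 is partly one of terms. A reader of SAP 1.6 alone would still be misled.

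The probabilities also have limits. The event includes stable disease, so true rates may be well above 20%, where 0/10 becomes rare. Section 6.2.7 plans to choose one RP2D for the expansion of about 45 patients; a single-agent expansion is optional, and only if niacin is chosen. The two-regimen figures apply only if both RP2Ds are tested.

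**Conclusion.** The point stands as a scope error in a stated rule. The condition and the pass are per regimen, while the only failure outcome is study-wide and contradicts the separate niacin assessment in the same paragraph. Followed literally, it lets 0/10 in one regimen, in either direction, end the other regimen's expansion and Part C.

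A regimen fails its own look with probability 60%, 35%, 11% or 2.8% at true rates of 5%, 10%, 20% or 30%. The literal wording does most harm when activity differs: 61% instead of 2.8% for a 30% regimen paired with a 5% regimen. These sizes rest on assumed rates, on both RP2Ds being tested and on independence. The contradiction in the text rests on none of them.

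**What to change.** 1. In the synopsis, protocol Sections 6.2.7 and 9.5.1, and SAP 1.1, replace the failure sentence with one saying that the expansion of that regimen will not be fully enrolled. In the same places, change *either expansion cohort* to *the expansion cohort of that regimen*.
2. Have the sponsor state explicitly whether a futility finding in Part A or Part B affects Part C. The documents do not settle this.
3. Change SAP 1.6 to name this look, per regimen, as the planned interim futility decision.
4. In the same edit, reconcile the stable-disease duration in Section 6.2.7 (about 8 weeks) with that in the synopsis, Section 9.5.1 and SAP 1.1 (about 16 weeks).

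The cost is wording in two documents. More patients may be enrolled in the surviving regimen than under a literal study-wide stop, but within the planned expansion maximum of 65.
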